3.1.2. Systemic Events

The systemic events assessed and recorded in the e-diary are fever, vomiting, diarrhea, headache, fatigue, chills, new or worsened muscle pain, and new or worsened joint pain, from Day 1 through Day 7, where Day 1 is the day of vaccination.

The derivations for systemic events will be handled in a way similar to the way local reactions are handled for presence of event, severity level, duration, and onset day.

The variables associated with the systemic events will be computed in a way similar to the way local reactions are computed (see Section 3.1.1).

- Presence (yes or no) of each systemic event on any day (Day 1 through Day 7).
- Maximum severity of each systemic event on any day (Day 1 through Day 7).
- Duration of each systemic event.
- Onset day of each systemic event.
- Presence (yes or no) of each severe systemic event on each and any of the 7 days.

The symptoms will be assessed by the participant as absent, mild, moderate, or severe according to the grading scale in Table 6.

Table 6. Systemic Event Grading Scale

	Mild (Grade 1)	Moderate (Grade 2)	Severe (Grade 3)	Potentially Life-Threatening (Grade 4)
Vomiting	1-2 times in 24 hours.	>2 times in 24 hours.	Requires IV hydration.	Emergency room visit or hospitalization for hypotensive shock.
Diarrhea	2 to 3 loose stools in 24 hours.	4 to 5 loose stools in 24 hours.	6 or more loose stools in 24 hours.	Emergency room visit or hospitalization for severe diarrhea.
Headache	Does not interfere with activity.	Some interference with activity.	Prevents daily routine activity.	Emergency room visit or hospitalization for severe headache.
Fatigue/tiredness	Does not interfere with activity.	Some interference with activity.	Prevents daily routine activity.	Emergency room visit or hospitalization for severe fatigue.
Chills	Does not interfere with activity.	Some interference with activity.	Prevents daily routine activity.	Emergency room visit or hospitalization for severe chills.
New or worsened muscle pain	Does not interfere with activity.	Some interference with activity.	Prevents daily routine activity.	Emergency room visit or hospitalization for severe new or worsened muscle pain.

Table 6. Systemic Event Grading Scale Mild Moderate Severe (Grade 1) (Grade 2) (Grade 3)

Potentially Life-Threatening (Grade 4) Prevents daily Does not interfere Some interference Emergency room visit New or worsened joint pain with activity. with activity. routine activity. or hospitalization for

severe new or worsened

joint pain.

Oral temperature will be collected in the evening, daily, for 7 days following vaccination (Day 1 through Day 7, where Day 1 is the day of vaccination) and at any time during the 7 days that fever is suspected. Fever is defined as an oral temperature of ≥38.0°C (≥100.4°F). The highest temperature for each day will be recorded in the e-diary.

Temperature will be measured and recorded to 1 decimal place. Temperatures recorded in degrees Fahrenheit will be programmatically converted to degrees Celsius for reporting.

Maximum temperature range over the period from Day 1 through Day 7 will be mapped into the ranges described in Table 7 for summary of maximum temperature. Fever will be grouped into ranges for the analysis according to Table 7.

Table 7. Scale for Fever

≥38.0°C to 38.4°C (100.4°F to 101.1°F)
>38.4°C to 38.9°C (101.2°F to 102.0°F)
>38.9°C to 40.0°C (102.1°F to 104.0°F)
>40.0°C (>104.0°F)

Note: Fever is defined as an oral temperature of \geq 38.0°C (\geq 100.4°F).

Temperatures <35.0°C and >42.0°C will be excluded from the analysis. If a participant reports a fever (or severity of fever) by accident, the correct temperature will be transcribed in a data handling memo to be included in the analysis, and the temperature that is confirmed as incorrect will not be included in the analysis.

3.1.3. Use of Antipyretic Medication

The use of antipyretic medication is also recorded in the e-diary from Day 1 through Day 7, where Day 1 is the day of vaccination. For the use of antipyretic medication from Day 1 through Day 7 after vaccination, the following endpoints and variables will be derived for analysis following the same rules as for local reactions (see Section 3.1.1), where applicable.

- Presence (yes or no) of use of antipyretic medication on each day (Day 1 through Day 7).
- Presence (yes or no) of use of antipyretic medication on any day (Day 1 through Day 7).

Page 19 of 40

- Duration (first to last day reported) of use of antipyretic medication.
- Onset day of use of antipyretic medication.

The use of antipyretic medication will be summarized and included in the systemic event summary tables but will not be considered a systemic event.

3.1.4. Adverse Events

Standard algorithms for handling missing AE dates and missing AE severity will be applied as described in the Pfizer Vaccine data standard rules. AEs will be collected from informed consent signing through 4 weeks following vaccination (Visit 4).

The following derivations will be included for each participant:

- Any AE reported.
- Any related AE reported.
- Any immediate AE (acute reactions were assessed for at least 30 minutes after study intervention administration).
- Any severe AE.
- Any life-threatening AE.
- Any AE leading to study withdrawal.
- Any AE leading to death.
- Any AESI.
 - A confirmed diagnosis of influenza.
 - A confirmed diagnosis of myocarditis or pericarditis occurring within 4 weeks after vaccination.
 - Confirmed COVID-19 diagnosis through the end of the study (clinical signs/symptoms and positive SARS-CoV-2 NAAT or rapid antigen test result).

3.1.5. Serious Adverse Events

SAEs will be collected from the time the participant provides informed consent through approximately 6 months after vaccination (Visit 6).

3.1.6. Laboratory Data

Abnormal troponin I laboratory values 2 days and 1 week after vaccination.

The following safety laboratory tests will be performed at the times defined in the schedule of activities section of the protocol. Additional laboratory results may be reported on these samples as a result of the method of analysis or the type of analyzer used by the clinical laboratory, or as derived from calculated values. These additional tests would not require additional collection of blood. Unscheduled clinical laboratory measurements may be obtained at any time during the study to assess any perceived safety issues.

Hematology	Chemistry
N/A	Cardiac troponin I

Clinically significant abnormal laboratory findings should be recorded in the AE CRF.

Additionally, the primary criterion for abnormality will follow the Pfizer safety rule book.

3.1.7. Electrocardiograms

An ECG abnormality is defined as any new abnormality that, as judged by a cardiologist, is consistent with probable or possible myocarditis or pericarditis, including:

- Sustained atrial or ventricular arrhythmias.
- Second-degree Mobitz type II or worse AV block or new bundle branch block.
- Diffuse ST-segment elevation or PR-segment inversion, compatible with pericarditis.

ECG data will be submitted to a central laboratory for measurement. The final ECG report from the central laboratory should be maintained in the participant's source documentation and be the final interpretation of the ECG recording. Any clinically significant changes from the baseline/Day 1 ECG may potentially be AEs and should be evaluated further, as clinically warranted.

3.2. Secondary Endpoints

- HAI titers for each strain, by study intervention group with qIRV.
- HAI titer fold rise for each strain, by study intervention group with qIRV.
- Presence of HAI seroconversion for each strain, by study intervention group with qIRV.
- Presence of HAI titers ≥1:40 for each strain, by study intervention group with qIRV.
- Presence of HAI seroconversion for all strains, by study intervention group with qIRV.
- Presence of HAI titers ≥1:40 for all strains, by study intervention group with qIRV.
- SARS-CoV-2—neutralizing titer for each strain, by study intervention group with a BNT162b2 dose.

- SARS-CoV-2—neutralizing titer fold rise for each strain, by study intervention group with a BNT162b2 dose.
- Presence of seroresponse for each strain-specific neutralizing titer, by study intervention group with a BNT162b2 dose.

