2.2.2. Secondary Estimands

The secondary estimands for the secondary objective (immunogenicity) will use the hypothetical strategy and estimate the vaccine immune response when an intercurrent event does not occur. In other words, the immune response is estimated in the hypothetical setting where participants follow the study schedule and protocol requirements as directed. It includes the following 5 attributes:

 Population: Participants 18 through 64 years of age and ≥65 years of age, as defined by the inclusion and exclusion criteria.

Variables:

- HAI titers for each strain, by study intervention group with qIRV, at each time point.
- HAI titer fold rise for each strain, by study intervention group with qIRV, from before vaccination to each time point after vaccination.
- Presence of HAI seroconversion for each strain, by study intervention group with qIRV, at each time point after vaccination.
- Presence of HAI titers ≥1:40 for each strain, by study intervention group with qIRV, before vaccination and at each time point after vaccination.
- Presence of HAI seroconversion for all strains, by study intervention group with qIRV, at each time point after vaccination.
- Presence of HAI titers ≥1:40 for all strains, by study intervention group with qIRV, before vaccination and at each time point after vaccination.
- SARS-CoV-2—neutralizing titer for each strain, by study intervention group with a BNT162b2 dose.
- SARS-CoV-2-neutralizing titer fold rise for each strain, by study intervention group with a BNT162b2 dose, from before vaccination to each time point after vaccination.
- Presence of seroresponse for each strain-specific neutralizing titer, by study intervention group with a BNT162b2 dose.
- Treatment condition: μg qIRV/ μg bivalent BNT162b2 (original*/Omi BA.4/BA.5), μg qIRV μg bivalent BNT162b2 (original*/Omi BA.4/BA.5), μg qIRV μg bivalent BNT162b2 (original*/Omi BA.4/BA.5), μg qIRV, στ μg bivalent BNT162b2 (original*/Omi BA.4/BA.5) administered concurrently in the opposite arm to licensed QIV, administered on Day 1.

- Intercurrent events: The following intercurrent events could impact the interpretation or the measurement of the immune response:
 - Not receiving the vaccine as randomized.
 - Not meeting the study inclusion/exclusion criteria.
 - Having major protocol deviations (received prohibited vaccine or treatment that may alter the immune response and subsequently impact the vaccine protection).

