 - Undergoing blood collection outside of the defined window (26 to 35 days, inclusive, after vaccination).

All data after intercurrent events, if collected, will be excluded.

- Population-level summary:
 - HAI GMTs at each time point and GMFRs from before vaccination to each time point after vaccination, and the proportion of participants achieving HAI seroconversion at each time point and the proportion of participants with HAI titers ≥1:40 before vaccination and at each time point after vaccination, will be estimated for each strain, by study intervention group with qIRV, for participants 18 through 64 years of age and ≥65 years of age separately.
 - SARS-CoV-2 GMT at each time point and GMFRs from before vaccination to each time point after vaccination, and the proportion of participants with seroresponse at 1, 4, and 8 weeks after vaccination, will be estimated for each strain by study intervention group with a BNT162b2 dose, for participants 18 through 64 years of age and ≥65 years of age separately.

*Original refers to the ancestral strain (Wuhan-Hu-1; USA-WA1/2020), also referred to in the protocol as the reference strain.

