2.3. Study Design

This is a Phase 1 randomized, open-label substudy to describe the safety and immunogenicity of up to 3 dose-level combinations of qIRV/bivalent BNT162b2 (original/Omi BA.4/BA.5). Approximately 360 participants will be enrolled across 2 age strata: approximately 180 participants 18 through 64 years of age and approximately 180 participants ≥65 years of age. The participants will be randomized equally (30 participants per group) to receive a dose of either:

 qIRV/bivalent BNT162b2 (original*/Omi BA.4/BA.5), at 1 of the 3 dose-level combinations shown in Table 2.

- μg qIRV,
- μg qIRV, or
- μg Bivalent BNT162b2 (original/Omi BA.4/BA.5) administered concurrently in the opposite arm to licensed QIV.

Table 2. Study Interventions and qIRV/Bivalent BNT162b2 (Original/Omi BA.4/BA.5) Dose-Level Combinations

Group Number	Dose-Level Combination	qIRV Dose	Bivalent BNT162b2 (Original/Omi BA.4/BA.5) Dose	Total modRNA Dose
1	1	CCI CCI	 μg, ie, μg of original BNT162b2 and μg of BNT162b2 Omicron (B.1.1.529 sublineage BA.4/BA.5) 	ССІ µg
2	2	ug, ie,	e μg, ie, μg of original BNT162b2 and μg of BNT162b2 Omicron (B.1.1.529 sublineage BA.4/BA.5)	μg
3	3	CCI ug, ie,	μg, ie, μg of original BNT162b2 and μg of BNT162b2 Omicron (B.1.1.529 sublineage BA.4/BA.5)	μg
4	N/A	ug, ie,	N/A	μg
5	N/A	CCI CCI	N/A	μg
6	N/A	N/A	(original/Omi BA.4/BA.5), administered concurrently in the opposite arm to licensed QIV	μg

As determined based on emergent data from ongoing clinical studies with BNT162b2, dose-level combinations 1 and/or 3 may be omitted from this study. Safety and immunogenicity data from studies previously conducted in participants of a similar age range having received 1 dose of BNT162b2 at a dose level of participants of a similar age as a control during analysis.

^{*}Original refers to the ancestral strain (Wuhan-Hu-1; USA-WA1/2020), also referred to in the protocol as the reference strain.

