6.2. Secondary Endpoints

6.2.1. Immunogenicity Endpoints

6.2.1.1. Main Analysis

- Estimand strategy: Hypothetical approach (Section 2.2.2).
- Analysis set: Evaluable immunogenicity population (Section 4).
- Analysis methodology: Descriptive summary statistics (Section 5.2.2).
- Analysis timing: 1, 4, and 8 Weeks after study intervention administration.
- Intercurrent events and missing data: All data collected after or at intercurrent events will be excluded. Antibody titers below the LLOQ will be treated as specified in Section 5.3.2. Missing data will not be imputed.
- Reporting results:
 - The SARS-CoV-2 GMT at each time point and GMFRs from before vaccination to
 each time point after vaccination, and the proportion of participants with seroresponse
 at 1, 4, and 8 weeks after vaccination, will be estimated for each strain, by study
 intervention group with a BNT162b2 dose, and separately by age group.
 - Descriptive statistics, including the sample size (n), GMTs, GMFRs, and 95% CI for the GMTs and GMFRs, will be presented for each strain by study intervention group with qIRV (Section 5.2.2), for participants 18 through 64 years of age and ≥65 years of age separately.
 - The proportion of participants achieving HAI seroconversion and the associated 2-sided Clopper-Pearson 95% CIs will be provided for each strain by study intervention group with qIRV, for participants 18 through 64 years of age and ≥65 years of age separately.
 - o The proportion of participants with HAI titers ≥1:40 before vaccination and at each time point after vaccination and the associated 2-sided Clopper-Pearson 95% CIs will be provided for each strain by study intervention group with qIRV, for participants 18 through 64 years of age and ≥65 years of age separately.
 - HAI GMTs for each strain and the associated 95% CIs will be plotted by study intervention group with qIRV, for participants 18 through 64 years of age and ≥65 years of age separately.
 - HAI seroconversion rate for each strain, along with the associated 95% CIs, will be presented by study intervention group with qIRV, for participants 18 through 64 years of age and ≥65 years of age separately.

- SARS-CoV-2 GMT at each time point and GMFRs from before vaccination to each time point after vaccination, and the proportion of participants with seroresponse at 1, 4, and 8 weeks after vaccination, will be provided for each strain by study intervention group with a BNT162b2 dose, and separately by age group.

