- SARS-CoV-2 GMTs for each strain and the associated 95% CIs will be plotted by study intervention group with a BNT162b2 dose, for participants 18 through 64 years of age and ≥65 years of age separately.
- o SARS-CoV-2 seroresponse rate for each strain, along with the associated 95% CIs, will be presented by study intervention group with a BNT162b2 dose, for participants 18 through 64 years of age and ≥65 years of age separately.
- Empirical RCDCs with HAI titers and SARS-CoV-2 neutralizing titers will be plotted separately for each strain by study intervention group, for participants 18 through 64 years of age and ≥65 years of age separately.
- Bar charts with the numbers, proportions of participants achieving HAI
 seroconversion, and associated 95% CIs at 4 weeks after study intervention
 administration will be provided for each strain by study intervention group with qIRV,
 for participants 18 through 64 years of age and ≥65 years of age separately.
- Bar charts with the numbers, SARS-CoV-2 seroresponse rate, and associated 95% CI at 4 weeks after study intervention administration will be provided for each strain by study intervention group with a BNT162b2 dose, for participants 18 through 64 years of age and ≥65 years of age separately.

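### The Substudy A SAP limits its HAI endpoints and main HAI tables to qIRV arms, so the randomised licensed-QIV arm (Group 6, about 60 of 360) is missing from them

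*SAP*

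**What the plan says.** In the Substudy A SAP, the first HAI endpoint in section 3.2 reads "HAI titers for each strain, by study intervention group with qIRV", and the other five HAI endpoints carry the same limit. Section 2.2.2 repeats it for the estimand variables ("HAI titers for each strain, by study intervention group with qIRV, at each time point") and for the HAI population-level summary ("will be estimated for each strain, by study intervention group with qIRV"). In 6.2.1.1 the GMT and GMFR results "will be presented for each strain by study intervention group with qIRV". The seroconversion and ≥1:40 tables, the GMT plot, the seroconversion-rate display and the week 4 bar chart are limited in the same way. One HAI output is not: "Empirical RCDCs with HAI titers and SARS-CoV-2 neutralizing titers will be plotted separately for each strain by study intervention group".

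For SARS-CoV-2, section 3.2 uses a different filter: "Presence of seroresponse for each strain-specific neutralizing titer, by study intervention group with a BNT162b2 dose".

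Section 2.3 lists the sixth arm as bivalent BNT162b2 ("original/Omi BA.4/BA.5) administered concurrently in the opposite arm to licensed QIV"). Table 2 marks its qIRV dose N/A.

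The current protocol has no such filter. Section 10.11.8.1 runs HAI on samples from all participants, 10.11.9.3.3 reports HAI by study intervention, and the Synopsis (Overall Design) names Fluzone SD as the QIV comparator for Substudy A.

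**The concern.** The two assay filters in 3.2 follow different principles. The SARS-CoV-2 filter keeps every arm that received a COVID-19 vaccine. The HAI filter keeps only the arms that received the investigational influenza vaccine, although all six arms received an influenza vaccine. Leaving the qIRV-alone arms out of the SARS-CoV-2 tables makes sense, because they had no COVID-19 vaccine. That reason does not carry over to Group 6 for HAI.

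Substudy A tests no hypothesis, so its immunogenicity results are read by comparing arm estimates and CIs. Under the current wording a reader could not set the qIRV estimates beside the licensed reference in the same table, although those participants were randomised alongside the qIRV arms and sampled at the same visits.

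**Working it through.** **1. Enrolment, reproduced.** SAP 2.3 and protocol 10.11.9.5 give 6 groups, 30 per group per stratum and 2 age strata. 6 × 30 = 180 per stratum and 180 × 2 = 360 in total, both matching the documents.

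**2. Size of the omitted arm.**
- Group 6: 30 × 2 = 60, and 60/360 = 16.7%.
- Groups 1 to 5, which the HAI tables cover: 5 × 30 × 2 = 300 of 360, or 150 of 180 per stratum.

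**3. Reach of the filter.**

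| SAP section | HAI items limited to qIRV arms |
|---|---|
| 2.2.2, variables | 6 of 6 |
| 2.2.2, population-level summary | 1 of 1 |
| 3.2, endpoints | 6 of 6 |
| 6.2.1.1, outputs | 6 of 7 (the distribution curves are the exception) |

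**4. The two filters set against Table 2.**

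| Assay | Arms given a relevant vaccine | Arms kept |
|---|---|---|
| SARS-CoV-2 | Groups 1, 2, 3, 6 | 4 of 4 |
| HAI | Groups 1 to 5 (qIRV) and 6 (QIV) | 5 of 6 |

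**5. Estimates lost from the main tables.** The strain list is redacted. I assume four HAI strains, because protocol section 6 describes qIRV as encoding four. The time points are baseline plus the SAP's "Analysis timing: 1, 4, and 8 Weeks after study intervention administration".
- Per strain and stratum: GMT 4 + GMFR 3 + seroconversion 3 + ≥1:40 4 = 14.
- Total: 14 × 4 strains × 2 strata = 112.
- Baseline and week 4 only: (2 + 1 + 1 + 2) × 4 × 2 = 48. This is the fairer count against the current protocol, which makes weeks 1 and 8 exploratory.

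**6. Where Group 6 still appears for HAI.**
- The distribution curves in 6.2.1.1 include it, but they give no GMT, GMFR or seroconversion estimate with a CI.
- Section 6.4, read literally, includes it, because it covers secondary immunogenicity endpoints for arms with a BNT162b2 dose. Those analyses are supplemental and split by baseline SARS-CoV-2 status.
- The mITT analysis in 6.2.1.2 reuses the main presentation, so it has the same gap.
- The HAI comparison list in 6.3.2 is partly redacted, so I draw nothing from it.

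**7. Fit with neighbouring text.** The HAI row of the SAP 2.2 objectives table restricts no arm, while its SARS-CoV-2 row is limited to recipients of the combination vaccine. The Substudy B SAP reports HAI by study intervention group without a qIRV filter (6.2.1.1) and uses its own QIV arm, Group 1, as an HAI comparator (6.2.1.2). I claim no contradiction from the 2.2.2 treatment condition, which does list the QIV arm: it may be a joint list for both assays, since 2.2.3, which covers SARS-CoV-2 only, has its own.

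**The case against.** The strongest counter-argument is about strains. SAP 2.2 defines the HAI panel by the strains recommended for recombinant or cell-based vaccines. The protocol's intervention table gives qIRV that same basis, but describes QIV only as carrying WHO-recommended strains. If the strains differ, a Group 6 column could flatter qIRV, and the restriction may be deliberate. This is plausible, but SAP A does not say it. A footnote would deal with it better than a silent omission.

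A second argument is that the secondary objective concerns the qIRV/bivalent BNT162b2 combinations, not a comparison with QIV. That does not explain the filter, because the filter keeps the qIRV-alone arms, Groups 4 and 5.

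Third, SAP A may modify the protocol's plan (2.1), and its version history ties it to amendment 2, whose text is not supplied. I therefore claim no departure from that amendment. The points that stand are the unexplained filter within SAP A and its poor fit with the current protocol.

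Fourth, 6.3.2 may contain a QIV contrast behind the redaction. If so, the practical loss is smaller, though a ratio or difference does not replace the arm's own estimates.

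It is also fair that protocol 10.11.4.1 lets the sponsor leave a group's samples unanalysed, so availability of the Group 6 results rests on the plan being carried through.

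**Conclusion.** The point holds. As written, SAP A's main HAI tables leave out the randomised licensed-vaccine comparator without giving a reason. The firm size is one arm of six, about 60 of 360. The counts of 112 or 48 missing estimates depend on the assumed four strains and on which time points are counted. The substudy is descriptive and HAI is a secondary endpoint, so no test or primary result is affected. The loss is in how the qIRV responses can be read, and it is worth correcting.

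**What to change.** In SAP A 2.2.2 (HAI variables and population-level summary), 3.2 and 6.2.1.1, replace 'with qIRV' by 'with qIRV or licensed QIV' for the HAI endpoints, so that Group 6 is tabulated in each age stratum. If the HAI assay strains differ from those in the licensed QIV, say so in a footnote to each table. The cost is a wording change and one more column per HAI table. No extra samples or assays are needed, because protocol 10.11.8.1 already plans HAI for all participants.
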